2.0 Approach

Study Aims: Our *long-term goal* is to increase uptake of CRC screening by informing and improving patient and provider discussion and decisions. The *main objective* of this study is to test whether providing patients and their providers with personalized messages about ACN risk results in higher screening uptake and higher decision quality (i.e., informed choice and receipt of the preferred screening test), compared to an approach that does not utilize ACN risk.

Aim 1: To measure the impact on patient decision quality and screening uptake of providing patients and their providers with personalized messages about the patient’s current risk of having advanced colorectal neoplasia (ACN).

Aim 2: To examine mediators and moderators of the interventions' effectiveness.

To achieve Aim 1, we will test the following hypotheses:

Primary hypotheses:

1. The proportion of patients who make a **high-quality decision** and **complete screening** at six months will be higher:

- 1.1 for patients who receive the personalized message than for those who do not, and
- 1.2 for patients whose providers receive the personalized message than for those whose providers do not.

Secondary hypotheses:

2. Among patients with low risk of ACN, the proportion who make a **high-quality decision** and **undergo a stool blood test (FIT)** by six months will be higher

- 2.1 for patients who receive the personalized message than for those who do not, and
- 2.2 for patients whose providers receive the personalized message than for those whose providers do not.

3. Among patients with high-average risk of ACN, the proportion who make a **high-quality decision** and **undergo a colonoscopy** by six months will be higher

- 3.1 for patients who receive the personalized message than for those who do not, and
- for patients whose providers receive the personalized message than for those whose providers do not.

3.0 Outcome Measures/Endpoints

Choice of Outcomes (PC-3, RQ-6): The primary outcomes are screening uptake and decision quality, each of which is essential to providing high-quality and patient-centered care.

- Screening uptake will be defined as performance of colonoscopy, FIT, or another approved screening test within six months after enrollment, as documented in the EHR, as in our previous study.⁵¹
- Decision quality will be defined by the multi-dimensional measure of informed consent (MMIC),⁵³ where a high-quality decision is one where the individual has adequate knowledge regarding the available options and undergoes the intervention that he or she has chosen or that fits his or her values ("value concordance") (PC-3)(RQ-6). Sepucha et al. (2018) recently used the MMIC approach in the Colorectal Cancer Screening Decision Quality Instrument (CRC-DQI).⁵⁴ We will identify knowledge and the patient's intention to be screened shortly after a provider visit (T2). We will measure concordance between the test choice at T2 and screening test underwent, if any, within six months after enrollment (T3).⁵⁵⁻⁵⁸

Increasing screening uptake is an essential outcome since screening saves lives (RQ-6). Providers and healthcare institutions aim to get their patients screened, heeding the ethical principle of beneficence.⁵⁹ Our partner healthcare institutions have repeatedly expressed their desire to increase their screening rates(RQ-6). We heard the same message – the importance of getting patients screened – from lay people participating in our public deliberation exercise (RQ-6).⁶⁰ Both patients and lay people have emphasized, from the beginning of our work on CRC screening, and in the public deliberation, the importance of improving decision quality about CRC screening.(RQ-6) Patients who view decision aids as part of our studies often learn about FIT for the first time, and often respond that there should be more public awareness of this option.(RQ-6)

We chose not to make decision conflict⁶¹ or shared decision-making distal outcomes, due to our focus on screening uptake and quality of decision making. However, we will collect these subjective measures as potential mediators for the primary outcomes. Improved outcomes may result from patients feeling

more supported in their decision making, as captured by the decision conflict scale,⁶¹ or feeling that they participated in shared decision making with their healthcare provider, as captured by one section of the CRC Screening Decision Quality Instrument developed by Sepucha et al (2018).⁵⁴

[figure not shown]
Theoretical framework: See **Figure 1:** (CI-1) Our theoretical framework is based on the Health Belief Model,⁶² which has been previously applied to research on CRC screening uptake.⁶³⁻⁶⁵ We expect the personalized message to impact patients at low risk, intermediate risk, and high-average risk, as described below:

- Low risk: For patients at low risk, *patients and providers* who view the personalized message will have increased perceived benefit of FIT and lower perceived barriers (i.e. concern over false negative result). These effects will increase the proportions of patients intending to be screened and to undergo FIT, and the proportion of providers who are willing to order FIT for patients who choose that test. Agreement between the patient's choice and the provider's ordered test will increase uptake (Hypothesis 1.1 and 2.1),⁴³ and higher concordance between patient choice and completed FIT will increase decision quality as measured by the MMIC (Hypotheses 1.2 and 2.2).(RQ-4)(CI-1)

- High-average risk: For patients with high-average risk, *patients and providers* who view the personalized message will have *increased perceived susceptibility* to CRC due to the high probability of a current ACN (22%) and *increased perceived benefit* of colonoscopy. These effects will increase the proportions of patients intending to be screened with colonoscopy, and the proportion of providers who order colonoscopy for patients who choose this test. This will result in increased uptake of screening (Hypotheses 1.1 and 3.1) and increase concordance between patient choice and performed test, which will increase decision quality as measured by MMIC (Hypotheses 1.2 and 3.2).(RQ-4)

- Intermediate risk: For patients with high-average risk, *patients and providers* who view the personalized message will have *increased perceived susceptibility* to CRC due to the significant probability of a current ACN (10%). This will increase patients' intention to be screened, providers' interest in discussing CRC screening and ordering a test, and successful follow through by patients, which will contribute to an increase in uptake of screening (Hypothesis 1.1) and in concordance and thus decision quality as measured by MMIC (Hypotheses 1.2).(RQ-4)(CI-1)

Figure 1

3.1 Primary Outcome Measures

The primary outcomes are screening uptake and decision quality, each of which is essential to providing high-quality and patient-centered care.

- Screening uptake will be defined as performance of colonoscopy, FIT, or another approved screening test within six months after enrollment, as documented in the EHR.
- Decision quality will be defined by the multi-dimensional measure of informed consent (MMIC),⁵³ where a high-quality decision is one where the individual has adequate knowledge regarding the available options and undergoes the intervention that he or she has chosen or that fits his or her values (“value concordance”). (PC-3, IR-4)
 - Knowledge (T2) will be assessed by a 12-item test made up of 6 multiple choice questions and 6 true-false questions that was updated from what we used in our previous study to reflect changes in screening guidelines. Adequate knowledge = 9 correct
 - Concordance (T3) will be measure between the test choice at T2 and screening test underwent, if any, within six months after enrollment(T3).

3.2 Secondary Outcome Measures

Patients: Data will be collected from patients at four time points: before they view the decision aid (T0); immediately after they view the decision aid (T1); aiming for 4-7 days after their appointment with their provider (T2); and six months after enrollment (T3).

- *Screening Intent* (T0, T1, T2): Intent to be screened for CRC with any test (“Screening Intent”), will be measured with 1 item: “Do you plan to get any type of colon test within the next 6 months?” and has a response option of: 5=Definitely, 4=Probably, 3=May or May not, 2=Probably not, and 1=Definitely not. This measure has been used in previous studies by our research team (PC-3, IR-4).^{51,52}
- *Test choice* (T0, T1, T2) (PC-3, IR-4): As in our previous studies:^{51,52}
 - For those who answer *Screening Intent* with “Definitely not,” “Probably not,” or “May or may not,” *Test Choice* is categorized as No screening.
 - Those who answer *Screening Intent* with “Probably” or “Definitely” have *Test Choice* categorized based on their answer to a single item: “If you have a colon test, which one would you choose?” Response options are: Stool test (FIT or Cologuard), Colonoscopy, Another test, or Don’t know.
- *Perceived CRC risk* (T0, T1, T2):
 - *Perceived personal CRC risk* will be assessed with a three-item scale, modified from items originally developed by Champion to measure perceived breast cancer risk^{78,79} and used by members of our team in multiple projects.^{51,52,69} Each item uses a four-point response option, where 1 = very unlikely and 4 = very likely, to assess participants’ beliefs about how likely they are to get CRC in the next 5 years, in the next 10 years and sometime during their lifetime. Cronbach alpha was 0.90 in our recent study. (PC-3, IR-4)
 - *Perceived comparative CRC risk* will be assessed with a single item measuring perceived comparative risk,⁶⁶ which asks “Compared to other women/men your same age, would you say your chance of getting colon cancer in the next 10 years is higher, about the same, lower, or don’t know?” (PC-3, IR-4)
- *Decision Conflict* (T0, T1, T2) will be assessed with the low literacy version of the Decision Conflict Scale, a ten-item instrument that assesses patients’ subjective feeling regarding the decision process over five areas and has been used widely in studies of decision aids (PC-3, IR-4).^{61,70}
- *Perceived Shared Decision Making* (T2) will be assessed with two measures. Patients will first answer five items adapted from the Shared Decision Making Process_4 Survey. This tool is a National Quality Foundation Measure used to assess the extent to which patients are involved in the decision-making process (PC-3, IR-4).⁵⁴ Patients will also respond to the 3-item CollaboRATE measure that assess three key areas of shared decision making; 1) explaining the health issue; 2)

asking for patient preferences; and 3) incorporating patient preferences into the decision. Each item uses likert response options ranging from “no effort was made” to “every effort was made”.^{73, 74}

- *Numeracy*: *Subjective numeracy* will be assessed at T0 with the Subjective Numeracy Scale (SNS) – short form, a validated instrument that involves 3 Likert-style questions.^{67, 71, 72}
- *Literacy* (T0) will be assessed using a 3-item health literacy scale (IR-4).⁷⁵
- *Demographic data* (T0) (including age, gender, income, education), as well as data on previous MD CRC screening recommendations, will be assessed utilizing a survey that has been used by our team and other researchers in multiple studies of CRC screening.^{51, 69}

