The email sent to participants will review the study procedures, who to contact with questions, and the unique link to their survey in Qualtrics. When the participant clicks the link, they will be taken to Qualtrics and the baseline survey (T0). After the participant completes T0, Qualtrics is programmed to stream the appropriate decision aid for that participant. When the decision aid completes, the post-intervention survey (T1) will display. Following completion of T1, the participant will be automatically sent a confirmatory email thanking them for completing this part of the study, reminding them of the next study contact, and who to contact with questions.

The baseline (T0) and post-intervention (T1) surveys are planned to take about 10 minutes each to complete. The control decision aid is approximately 10 minutes long and the intervention decision aid is approximately 15 minutes long (see Appendix for T0 and T1 surveys).

Research assistants will start contacting participants approximately four days after the participant's provider visit to complete the post-provider visit (T2) survey. Research assistants will aim to start collecting the T2 data four days after the provider visit; however, if the patient requests contact sooner due to scheduling conflicts, the research assistant will contact the patient as requested. Research assistants will first attempt to collect the T2 data over the phone; however, if unsuccessful or if the participant prefers, the research assistant can email the participant a link to complete the survey online in REDCap.

The post-provider visit (T2) survey is planned to take about 15 minutes (see Appendix for T2 survey).

Research assistants will start contacting participants 6 months after study enrollment to complete the 6-month follow-up (T3) survey. Research assistants will first attempt to collect the T3 data over the phone; however, if unsuccessful or if the participant prefers, the research assistant can email the participant a link to complete the survey online in REDCap.

The 6-month follow-up (T3) survey is planned to take about 15 minutes (see Appendix for T3 survey).

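### A patient screened before the T2 survey can be scored as having chosen 'No screening', because T2 asks only about future tests and no scoring rule covers tests already done

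*Combined protocol and SAP*

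**What the plan says.** Section 3.1 defines a high-quality decision as adequate knowledge at T2 (9 correct on the 12-item test) plus concordance: "Concordance (T3) will be measure between the test choice at T2 and screening test underwent, if any, within six months after enrollment(T3". Uptake is counted "within six months after enrollment, as documented in the EHR", so the window opens at enrollment, before the provider visit.

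Section 3.2 gives the T2 test choice in two steps. The gate is the intent item, "Do you plan to get any type of colon test within the next 6 months", with five answers from 'Definitely' to 'Definitely not'. For the three lowest answers, test choice "is categorized as No screening". Only those answering 'Probably' or 'Definitely' are classified by the choice item: "Response options are: Stool test (FIT or Cologuard), Colonoscopy, Another test, or Don’t know". Neither item has an answer for a test already done.

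On timing, section 3.2 aims T2 at 4-7 days after the visit. Section 7.2 says "Research assistants will aim to start collecting the T2 data four days after the provider visit", by phone first and by emailed link if that fails or the patient prefers. No latest date is given.

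Two other provisions come close. Section 3.3 asks patients whose intent or choice changed since T1 to explain why. Section 7.2 has research assistants check self-reported uptake against the EHR. Neither is linked to the scoring of test choice.

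**The concern.** The two halves of concordance cover different periods. The test undergone counts from enrollment; the test chosen is inferred from plans looking forward from T2. A test done in between enters the first half and can remove the patient from the second.

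The answer that triggers this is a natural one. By the intervals in section 1.0, FIT is annual, Cologuard three-yearly and colonoscopy ten-yearly, so a person just screened is not due again within six months. FIT is done at home without preparation, so it is the test most likely to be finished by T2. The gap nevertheless applies to any test done between enrollment and T2.

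At stake is the decision-quality outcome, which enters primary hypotheses 1.1 and 1.2. The patients at risk chose a test, understood it and completed it quickly. T2 intent would also read low for some of those who acted fastest, which matters for any Aim 2 mediation analysis that uses it.

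**Working it through.** **1. Tracing one patient through the rules.** Take a patient with adequate knowledge who chose a stool test at T1 and returned the FIT before T2.

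| Item | Rule | Result |
|---|---|---|
| Uptake | Test since enrollment, in EHR (3.1) | Yes |
| T2 intent, answered literally | Plans for the next 6 months (3.2) | 'Probably not' |
| T2 test choice | Three lowest answers (3.2) | No screening |
| Concordance | T2 choice against test done (3.1) | Discordant |
| Decision quality | Knowledge and concordance (3.1) | Fail |

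If the same patient answers 'Probably' or 'Definitely' and picks the stool test, the result is concordant. A patient with inadequate knowledge fails either way. The miscoding is therefore conditional.

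**2. Reproducing the plan's sample size (section 10.0).** Two-sided alpha 0.05, 80% power, each main effect treated as a two-group comparison.

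- Informed choice, 20% vs 30%. The pooled two-proportion formula gives 294 per level, 588 in total. The Wald form is (1.960 + 0.842)² × [1/(0.2×0.8) + 1/(0.3×0.7)] / (ln 1.714)² = 297.5 per level, 595 in total. The plan states 604.
- Uptake, 30% vs 40%. The same formulas give 712 and 718. The plan states 732.
- Inflation. Design effect 1 + (8 − 1) × 0.05 = 1.35; 732 × 1.35 = 988.2; 988.2 / 0.9 = 1098. The plan states 1100.

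The plan's figures reproduce to within 3%.

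**3. Power for decision quality without miscoding.** 1100 × 0.9 = 990 analysed; 990 / 1.35 = 733 effective, or about 367 per level. For 20% vs 30%, power is 88.0%. It exceeds 80% because the trial is sized on uptake.

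**4. Effect of miscoding.** Let f be the share of true high-quality decisions coded No screening at T2. It is the share whose test was done before T2, multiplied by the share of those who answer 'May or may not' or lower. The documents give neither factor, so every f below is an assumption. The observed rate is p × (1 − f).

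| f without message | f with message | Observed rates | Difference | Power |
|---|---|---|---|---|
| 0 | 0 | 20.0% vs 30.0% | 10.0 points | 88.0% |
| 2% | 2% | 19.6% vs 29.4% | 9.8 | 87.1% |
| 5% | 5% | 19.0% vs 28.5% | 9.5 | 85.8% |
| 10% | 10% | 18.0% vs 27.0% | 9.0 | 83.2% |
| 20% | 20% | 16.0% vs 24.0% | 8.0 | 77.4% |
| 30% | 30% | 14.0% vs 21.0% | 7.0 | 70.4% |
| 2% | 5% | 19.6% vs 28.5% | 8.9 | 80.6% |
| 5% | 10% | 19.0% vs 27.0% | 8.0 | 73.1% |
| 10% | 20% | 18.0% vs 24.0% | 6.0 | 51.4% |

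With equal miscoding, power stays above the planned 80% up to at least f = 10% and is below it by f = 20%. Unequal miscoding costs more at much smaller values.

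**The case against.** **The T2 form is not available.** The surveys are in separate attachments (section 14.0), and the form may hold a skip or an 'already done' answer. This stands, and it rules out saying that such patients will be miscoded. It does not close the gap, because sections 3.1 and 3.2 define the outcome and a skip would still need a scoring rule there.

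**The number may be small.** T2 is aimed at 4-7 days after the visit, leaving little time to return a kit. This also stands, with the limit that the window is a target: late interviews and emailed surveys raise the number.

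**The case can be detected.** A patient who intended screening at T1 and answers 'not' at T2 is asked why (section 3.3), and EHR test dates exist. True, but detection without a stated rule leaves the recoding of a primary outcome to be decided after the data are seen.

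**There is spare power.** As the working shows, modest equal miscoding leaves decision quality above 80%. Uptake itself is unaffected.

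**A reader might infer** that the error must be larger in the personalized arms, since the message favours FIT for low-risk patients (53% in the section 1.0 table), and so biases the trial against its own intervention. The documents do not establish this. The message also steers high-average patients (15%) toward colonoscopy, every arm's decision aid presents FIT, and no FIT share by arm is given. The low-risk FIT hypothesis, the most exposed, is declared exploratory in section 10.0.

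**Conclusion.** The concern holds in a limited form. Applied as written, sections 3.1 and 3.2 can score a patient who was screened before T2 as having chosen no screening, and no passage prevents it. This is a stated rule giving a wrong result in a foreseeable case on a primary outcome. It is not certain for every early completer: it requires a low answer to the intent item, and it changes the result only where knowledge was adequate.

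The size is unknown. On assumed equal miscoding of 2-10%, the loss is 0.2-1.0 points of a 10-point effect and about 1-5 points of power. Bias toward no effect through more early FIT in the message arms is plausible but unproven; at 5% vs 10% it would take the effect to 8.0 points and power to about 73%. These results rest on the plan's 20% and 30% rates, its intraclass correlation and attrition, and the assumed values of f.

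**What to change.** Before outcome analysis, add to section 3.1:

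- Where the EHR test date precedes the T2 interview, T2 test choice is not coded No screening on the basis of the intent item. Concordance uses the T1 (post-decision-aid) choice instead, identically in all arms.
- The recorded T2 intent value stays unchanged.
- Two sensitivity analyses are reported: one with the coding as now written, and one excluding tests done before T2.

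If T2 is still being collected and the form lacks it, add one item asking whether a test has been done since enrollment and which one.

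Two alternatives are best avoided. Asking early completers afterwards which test they had chosen invites an answer that matches the test done and makes concordance nearly automatic. Resetting their intent to 'Definitely' overwrites a measured variable.

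The cost is a coding rule on data the plan already collects, plus at most one survey item. The downside is that for these patients choice is measured before the visit, so the visit's influence on choice, which bears on hypothesis 1.2, is not captured. The sensitivity analyses show whether that matters.

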10.0 Statistical Considerations

Sample Size Justification: This trial is powered for the two primary hypotheses. For Aim 1, we expect exposure to either personalized message will increase uptake from 30%, which was the uptake at six months seen in our current PCORI project, to 40% and the combined effect to be additive (i.e. no interaction between the interventions). We believe a 10% increase in uptake is a minimally important difference to detect. An earlier study found that patients who viewed a personalized message about risk of colorectal cancer had a 9% higher uptake than did those who viewed a non-personalized message (CI-2).⁴¹ We believe our intervention will have greater impact, due to its encouraging low-risk individuals (50% of patients)⁷ to use a non-invasive test. An earlier study found that individuals due for screening who were offered a non-invasive test had a 31% higher rate of screening than those offered just colonoscopy (69% vs. 38%)(CI-2).⁵ To detect an effect of 10% increase (odds ratio of 1.55) with a power

of 80% (two-sided $\alpha=0.05$) a sample size of 732 subjects (183 per group) is needed for the Wald test for either patient or provider message main effect in a logistic model if patient outcomes were independent. To account for clustering due to randomization by provider, we inflate the sample size based on the design effect. We assume an intraclass correlation of .05 for provider, and average number of subjects per provider of 8. (RC-3) We will allow for an attrition rate of 10%. This results in a final sample size of 1100 (275 per group). For the informed choice outcome, we expect exposure to either personalized message would increase informed choice from 20%, the outcome in our current PCORI project, to 30% (odds ratio of 1.71) and the effect to again be additive. This leads to an initial sample size of 604 total (151 per group) before accounting for inflation and attrition, which is less than for uptake. Thus, the sample size needed for both outcomes is 1100 (275 per group, 130 providers). These recruitment goals are readily achievable based on the INFORM study. Aim 2 is considered exploratory because we don't have sufficient preliminary data to estimate all effect sizes; however, we will have sufficient power for some hypotheses. (IR-1)

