Analytic plan: Preliminary analyses will compare baseline demographic information across the four groups using means and standard deviations for continuous variables and frequency distributions for categorical variables. We will adjust for those characteristics in subsequent analyses if significant differences emerge at a conservative level for inclusion of a covariate ($p<.20$). Characteristics of participants who don't complete T1 and/or T2 will be compared with those who remain to determine what biases may exist. The above analyses will be conducted using ANOVA, chi-square tests, or exact or non-parametric equivalents. If there appear to be biases in dropout, we will conduct pattern mixture models analyses to see how the results could change based on the missing data assumption (IR-5, MD-2, MD-3, MD-4). Primary analysis of outcomes will employ an intent-to-treat analysis. For Aim 1, our primary hypotheses will be tested using logistic regression models with the outcomes of informed choice and uptake (both yes/no outcomes) and main effects for: 1) patient receipt of personalized message; and 2) provider receipt of personalized message. A random effect for provider will be included to account for the clustered randomization. We will test for an interaction effect, but do not expect one so have not powered the study for an interactive effect. The secondary hypotheses (planned subgroup analyses with low risk group) will be tested using the same model type (HT-2, HT-3). The secondary hypotheses are considered exploratory. For Aim 2, mediation effects (RQ-6) will be estimated in a logistic regression setting, fitting the appropriate mediation models using MPlus⁷⁶ and then testing indirect effects using the percentile bootstrap approach to estimate the indirect effect.⁷⁷ For primary analyses, we will fit models that estimate the effects of either or both of the interventions relative to control. Moderators (RQ-4, HT-1, HT-2, HT-3, HT-4) will be identified by significant interaction terms in the regression models from Aim 1.

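### Does coding patients who 'may or may not' be screened as having chosen no screening distort the informed-choice outcome?

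*Combined protocol and SAP*

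**What the plan says.** - **Test choice (Section 3.2).** Intent to be screened within six months is a five-point item. The two negative answers are pooled with the midpoint: a patient answering either of the negatives "or “May or may not,” *Test Choice* is categorized as No screening". Those who answer *Probably* or *Definitely* are classified by a second item: "Response options are: Stool test (FIT or Cologuard), Colonoscopy, Another test, or Don’t know". The plan says this follows the team's previous studies.
- **Concordance (Section 3.1).** "Concordance (T3) will be measure between the test choice at T2 and screening test underwent, if any, within six months after enrollment(T3"). A high-quality decision needs adequate knowledge (9 correct of 12) and a patient who "undergoes the intervention that he or she has chosen or that fits his or her values".
- **Objective (Section 2.0).** The aim is "higher decision quality (i.e., informed choice and receipt of the preferred screening test"). The primary hypothesis is that the proportion making a "high-quality decision and complete screening at six months will be higher" with the messages.
- **Sizing and model (Section 10.0).** Either message "would increase informed choice from 20%, the outcome in our current PCORI project, to 30"%. The primary hypotheses are tested with "logistic regression models with the outcomes of informed choice and uptake (both yes/no outcomes").

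No table gives the concordance score for each combination of choice and test undergone. In particular, the score for choosing no screening and having no test is not stated, nor is the score for *Don't know*.

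**The concern.** The midpoint of an intent scale is indecision, not refusal. If a no-screening choice followed by no test is concordant, a knowledgeable patient who never made up their mind is credited with a high-quality decision by doing nothing. The same patient, if later screened, is scored discordant although no stated choice was contradicted. Intenders who cannot name a test, by contrast, keep their own category.

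The theoretical framework in Section 3.0 expects the messages to raise intention to be screened. Each patient who moves from undecided to a test choice would leave a group that succeeds by inaction and join one that succeeds only by completing the chosen test. The effect on informed choice could be understated, or even change sign. Informed choice is sized and modelled as an outcome in its own right, so this would matter.

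**Working it through.** **1. The plan's own figures.** A two-arm Wald test on the log odds ratio (two-sided 0.05, 80% power), for 20% against 30%: (1.960 + 0.842)² × [1/(0.2×0.8) + 1/(0.3×0.7)] / (ln 1.714)² = 7.849 × 11.012 / 0.2905 ≈ 297.5 per arm, or 595 in total. The plan gives 604 (1.5% apart). The same formula for uptake, 30% against 40%, gives 718 against 732. With ICC 0.05 and 8 patients per provider the design effect is 1 + 7×0.05 = 1.35, and 732 × 1.35 / 0.90 = 1098, against the stated 1100. Informed choice alone would need 604 × 1.35 / 0.90 ≈ 906, so it does not drive the sample size.

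**2. Model for the coding.** Let N be the share coded as no screening, I = 1 − N the intenders, s uptake among intenders, u uptake among N, m the share of screened intenders who get their chosen test, and k the share with adequate knowledge (equal across arms unless stated). From Section 10.0, control uptake is I·s + N·u = 0.30 and control informed choice is 0.20. The documents give none of N, u, m or the size of the shift. Assumed ranges: N = 15, 25, 40%; u = 5, 10, 15%; m = 100% or 80%; 5 or 10 points moving from undecided to a test choice.

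- *Reading A* (no choice and no test is concordant): informed choice = k·[I·s·m + N·(1−u)].
- *Reading B* (receipt of a test required): informed choice = k·I·s·m.

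**3. Central case, Reading A** (N = 25%, u = 10%, m = 1).

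- Control: I·s = 0.30 − 0.025 = 0.275, so s = 0.367. Concordance = 0.275 + 0.225 = 0.50 and k = 0.20/0.50 = 0.40. Unscreened no-screening patients make up 0.225/0.50 = 45% of successes.
- Ten points move, s fixed: concordance = 0.85×0.367 + 0.15×0.90 = 0.447; informed choice 17.9% (−2.1).
- Ten points move, uptake 40%: concordance = (0.40 − 0.015) + 0.135 = 0.52; informed choice 20.8% (+0.8).

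**4. Ranges over the grid, Reading A** (points). The last column gives no credit to the undecided and keeps k as calibrated.

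| m | Move | Follow-through | As coded | Undecided not credited |
|---|---|---|---|---|
| 100% | 10 | fixed | −1.5 to −2.8 | +1.4 to +1.6 |
| 100% | 10 | uptake 40% | +0.3 to +1.5 | +3.2 to +5.7 |
| 100% | 5 | fixed | −0.7 to −1.4 | +0.7 to +0.8 |
| 100% | 5 | uptake 40% | +1.7 to +3.2 | +3.1 to +5.3 |
| 80% | 10 | fixed | −1.9 to −3.6 | +1.2 to +1.5 |
| 80% | 10 | uptake 40% | −0.6 to +0.4 | +2.8 to +5.3 |
| 80% | 5 | uptake 40% | +1.1 to +2.5 | +2.7 to +4.9 |

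At full match, unscreened no-screening patients are 31–59% of control successes. This is an upper bound for the undecided part.

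**5. Reading B.** Recoding the midpoint changes nothing, because no unscreened patient can succeed and a screened one in N has no chosen test to match. The change in informed choice is 0.20 × [(I·s after)/(I·s before) − 1]. Central case at 40% uptake: 0.20 × (0.385/0.275 − 1) = +8.0 points; over the grid with 10 points moving, +7.2 to +9.6. The plan expects +10. Reading A gives −0.6 to +1.5 for the same move and uptake (m = 80% or 100%). Reading B implies adequate knowledge in 0.20/(0.30 − N·u) = 68–83% of controls at full match, against 40% in the central case under Reading A.

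**6. Direction under Reading A.** Suppose the messages raise only knowledge, by 10 points. In the central case, informed choice rises 0.10 × 0.50 = 5.0 points as coded. With the undecided not credited it rises 0.10 × 0.275 = 2.8 points if all of N are undecided, or 0.10 × (0.275 + 0.1125) = 3.9 if half are. Here the plan's coding enlarges the effect.

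**7. Cost to the planning rate.** With the central k, the recoded control rate would be 0.40 × 0.275 = 11.0% if all of N are undecided, or 0.40 × 0.3875 = 15.5% if half are. Neither is the 20% on which Section 10.0 rests.

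**The case for a change.** The best case for a change is that Reading A fits several phrases. The words *if any* in the concordance rule allow for patients with no test. Fit with the patient's values admits an informed refusal. If a high-quality decision already required a test, adding completed screening to the hypothesis would be redundant.

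The mechanism is also sound. Moving a share x of patients changes the outcome by k·x·(c − (1 − u)), where c is intenders' completion of the chosen test. This is negative whenever c + u < 1. Suppose the earlier project's mean intent of 3.94 and 30% uptake carry over to T2, and intenders complete at least as often as the undecided. Score intenders (share q) at most 5, undecided (share r) 3 and the rest at most 2: then 3q + r ≥ 1.94, so q + r ≥ 0.647, and c + u ≤ 0.60/0.647 ≈ 0.93. On those assumptions, movement alone lowers the score.

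What stands is that the cell is unscored and that, under Reading A, crediting indecision is awkward. The premise itself is not established. The objective names receipt of the preferred test, the definition speaks of undergoing an intervention, and the low-risk paragraph in Section 3.0 ties decision quality to a completed FIT. Redundant wording is weak evidence, since Section 3.1 lists uptake and decision quality as separate outcomes. The comparison in step 5 leans toward Reading B but does not settle it, because its inputs are assumed and it needs high knowledge.

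A sign change is also hard to reach under the plan's own alternative. At 40% uptake and full match no grid cell is negative. A negative result needs unchanged follow-through, which Sections 3.0 and 10.0 do not expect, or 80% match together with a 10-point move.

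**Conclusion.** No change to the plan follows. The concern depends on a scoring rule that the documents do not state and that some of their wording contradicts. If receipt is required, the coding has no effect. If it is not, the assumed inputs give between −3.6 and +3.2 points on informed choice when patients move out of indecision with knowledge unchanged, and an enlarged effect when knowledge alone rises. The coding therefore has no fixed direction of bias.

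Its reach is narrow. Uptake does not use the T2 choice. An undecided patient cannot succeed on the joint hypothesis under either coding: unscreened, the patient fails on completion; screened, there is no chosen test to match.

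The alternative coding is a trade-off. Asking about a plan within six months and treating anything short of *Probably* as no chosen test is a defensible, prespecified split that keeps comparability with the earlier studies. Replacing it removes the source of the 20% planning rate. It also cures only part of the mechanism, because a move from *Probably not* to *Probably* has the same arithmetic.

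The unscored cells are missing detail of the kind settled when the outcome derivation is written. *Don't know* names no test to match, so not concordant is its natural score. This conclusion assumes that the scores are fixed before outcomes are compared by group, and that the report states them.
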